Given that the available evidence supports administration of thoracic radiotherapy with either the first or second cycle of systemic chemotherapy, the study was amended on September 15, 2009. Investigators now choose when radiotherapy will start at the time of patient registration. This will allow additional time for investigators to perform sophisticated radiotherapy treatment planning in select patients without delaying the administration of chemotherapy. The timing of radiotherapy delivery (e.g. cycle 1 vs cycle 2) will be incorporated as a stratification factor. Additionally, as of February 20, 2013, patients will be allowed to receive one cycle of chemotherapy prior to registering on CALGB 30610. These patients will then receive the radiotherapy during their second cycle of chemotherapy (their first cycle of protocol therapy).

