5.6 Registration to Companion Studies

There are two substudies within CALGB 30610. The correlative science study must be offered to all patients enrolled on CALGB 30610; the quality of life study must be offered to all English-speaking patients enrolled on CALGB 30610 (although patients may opt to not participate). These substudies do not require separate IRB approval. **Note: The quality of life substudy, CALGB 70702, closed to accrual on August 30, 2017. Therefore, no further patients will be enrolled on the quality of life substudy.**

The substudies included within CALGB 30610 are:

- CALGB 150712: Correlative Science Studies in CALGB 30610 ([Section 10.1](#))
If a patient answers "yes" to "My specimen(s) may be used for the research described above" question #1 in the model consent, they have consented to participate in the substudy described in [Section 10.1](#). The patient should be registered to CALGB 150712 at the same time they are registered to the treatment trial (30610). Samples should be submitted per [Section 6.3](#).
- CALGB 70702: Quality of Life Studies in CALGB 30610 ([Section 10.2](#))

As of August 30, 2017, accrual to CALGB 70702 has been met. **Therefore, after August 30, 2017, not further patients will be registered to CALGB 70702.**

Only English-speaking patients may participate in the QOL companion. If a patient answers “yes” to “I choose to take part in the Quality of Life study and agree to complete the Quality of Life questionnaires” question #5 in the model consent, they have consented to participate in the substudy described in Section 10.2. The patient should be registered to CALGB 70702 at the same time they are registered to the treatment trial (CALGB 30610).

Note: Patients that are registered on CALGB 30610 after they receive one cycle of chemotherapy are NOT eligible for the companion studies.

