6.3 Specimen Submission for Correlative Studies

All participating institutions must ask patients for their consent to participate in the correlative science studies in CALGB 30610 (CALGB 150712), although patient participation is optional. Patients registered to CALGB 30610 after receiving one cycle of chemotherapy will not participate in the correlative science substudy. Rationale and methods for the scientific components of these studies are described in [Section 10.1](#).

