10.0 COMPANION STUDIES

There are two substudies within CALGB 30610. Patients who receive one cycle of chemotherapy prior to registering on CALGB 30610 will NOT be offered participation in either companion study.

The correlative science and the quality of life studies must be offered to all patients enrolled on CALGB 30610 (although patients may opt to not participate). These substudies do not require separate IRB approval. The substudies included within CALGB 30610 are:

- CALGB 150712: Correlative Science Studies in CALGB 30610
- CALGB 70702: Quality of Life Studies in CALGB 30610, **closed to accrual as of 8/30/17**

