The trial is designed to have adequate power to test the null hypothesis $H_0: \log(\lambda_1 / \lambda_{2/3}) = 0$ versus the alternative hypothesis $H_a: \log(\lambda_1 / \lambda_{2/3}) \geq 1.3$ for the comparison of overall survival between the remaining experimental arm (arm 2) and the standard arm (arm 1). The power analysis is based on the following assumptions: (1) the 2-year overall survival rate of the remaining experimental arm (arm 2) is 57.3% and that of arm A is 48.5%. Under exponential survival distribution, the median survival for the remaining experimental arm is 29.9 months and for the standard arm is 23 months, or a hazard ratio of 1.3 (λ_1 / λ_2) for the standard arm to the remaining experimental arm; (2) an accrual length of 6 years; (3) 303 eligible patients in the standard arm and 303 eligible patients in the remaining experimental arm; (4) additional follow-up of 2.5 years after the last enrollment; (5) a two-sided significance level of 0.05. Under these assumptions, at the time of final analysis, at least 483 deaths are anticipated under alternative hypotheses for the two remaining comparative arms. Without taking into account the expected minimal loss of power due to interim analyses, the power in detecting the survival improvement for the remaining experimental arm (arm 2) as compared to the standard arm is at least 81.9% using a stratified log-rank test.

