15.6 Correlative Studies (CALGB 150712)

In the main treatment study, a total of 303 patients will be randomized to the standard control arm (arm A) and the remaining experimental arm (arm B or arm C, depending on the toxicity data from an initial cohort, the more toxic experimental arm will be dropped). These patients will be followed for disease progression and survival for at least 3 years after enrollment. All patients will be invited to join the correlative science substudies. Samples from consenting patients will be collected at baseline (before treatment initiation), day 21 (pre-chemotherapy), at first follow-up after completion of all protocol treatment, and at the time of disease recurrence. The laboratory data, including measures of all biomarkers described in the protocol, will be sent to the Alliance Statistics and Data Center, where the laboratory data will be merged with the clinical data and analyzed by Alliance statisticians.

Power Analysis for the First Correlative Science Substudy (Section 10.1.1):

The primary objectives of this first correlative science substudy are (i) to test whether higher-dose, accelerated radiation therapy (arm B or C) will cause a larger rise in circulating markers of endothelial damage than hyperfractionated and accelerated radiotherapy (arm A), and (ii) to determine whether the baseline biomarker profile, or changes in the profile during treatment, correlate with clinical outcome as judged by objective response rate, progression free survival, and overall survival.

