With allowance of 20% patient loss due to consent, ineligibility, and specimens of poor quality, we assume that 264 patients on arm A and 264 patients on arm B/C will provide evaluable circulating biomarkers for final analysis. With regards to the first primary objective, we assume the transform of biomarker count difference between post-treatment initiation and baseline follows approximately a normal distribution so that a 2-sample t test would be appropriate. At a 2-sided significance level of 0.05, the study has 90% power to detect a 0.274 standard deviation of cell count difference between the two treatment arms on log scale. With regards to the second primary objective, for the purpose of power analysis, the correlation of the biomarker (baseline or change scores of post-initiation of treatment against baseline) with response rate, 2-year FFS and 2-year OS will be tested for each arm using logistic regression with a single continuous predictor. At a 2-sided significance level of 0.05, the study has at least 90% power to detect a 6% increase of response rate from 80% at the mean of the biomarker to 86% at one standard deviation above of the mean. Similarly, the study has at least 90% power to detect an 11% increase of 2-year FFS from 40% at the mean to 51% at one standard deviation above of the mean, to detect an 11% increase of 2-year OS from 50% at the mean of a biomarker to 61% at one standard deviation above of the mean.

Power Analysis for the Second Correlative Science Substudy (Section 10.1.2):

The primary objective of the second correlative substudy is to evaluate the correlation of several serum markers at baseline or their changes against baseline with response rate (RR), failure free survival (FFS), and overall survival (OS) in small cell lung cancer. They include neuron-specific enolase (NSE), carcinoembryonic antigen (CEA), BB isoenzyme of creatine kinase (CK-BB), angiogenic factors Interleukin 8 (IL-8) and Vascular Endothelial Growth Factor (VEGF), stem cell factor (SCF), granulocyte-macrophage-colony stimulating factor (GM-CSF), and tumor

hypoxia marker osteopontin. The correlation tests are considered exploratory and the Type I errors will not be adjusted for multiple comparisons.

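### The evaluable numbers and 90% power stated in section 15.6 for the first two biomarker substudies do not follow from 303 patients per arm, and they make no allowance for patients barred after a prior chemotherapy cycle

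*Combined protocol and SAP*

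**What the plan says.** Section 15.6 describes the source of samples for CALGB 150712 as the randomised patients of the two remaining arms: "All patients will be invited to join the correlative science substudies". Section 15.3 puts that population at "303 eligible patients in the standard arm and 303 eligible patients in the remaining experimental arm".

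For the first substudy, 15.6 proceeds "With allowance of 20% patient loss due to consent, ineligibility, and specimens of poor quality" to 264 evaluable patients per arm, and concludes that "the study has 90% power to detect a 0.274 standard deviation of cell count difference between the two treatment arms on log scale". It also claims at least 90% power within each arm for three logistic regressions per SD of the biomarker: response 80% to 86%, 2-year FFS 40% to 51% and 2-year OS 50% to 61%. For the second substudy it assumes 230 per arm, described as 70%. It claims at least 90% power for response 80% to 86%, FFS 40% to 52% and OS 50% to 62%.

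Section 1.2 records that "as of February 20, 2013, patients will be allowed to receive one cycle of chemotherapy prior to registering on CALGB 30610". Three operative sections then exclude these patients:
- Section 5.6: "Patients that are registered on CALGB 30610 after they receive one cycle of chemotherapy are NOT eligible for the companion studies".
- Section 6.3: "Patients registered to CALGB 30610 after receiving one cycle of chemotherapy will not participate in the correlative science substudy".
- Section 10.0: "Patients who receive one cycle of chemotherapy prior to registering on CALGB 30610 will NOT be offered participation in either companion study".

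**The concern.** The invitation sentence in 15.6 contradicts three other sections of the same protocol. The prior-cycle route is a level of the start-time stratification factor in 5.5 and 15.2, so section 15 plans for these patients elsewhere. In 15.6, which turns randomised patients into evaluable samples, they do not appear. The exclusion also follows from the sampling plan: 6.3.1 and 15.6 require a baseline sample before treatment starts, and the analyses use change from baseline.

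The evaluable numbers also fail a simpler check, because the stated loss and yield do not turn 303 into 264 and 230.

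At stake is how the results will be read. Section 15.6 lists the between-arm test of endothelial-damage markers as a primary objective of the first substudy. A null result would be reported beside a 90% power figure that the section cannot reproduce from its own inputs. The results would also be described as covering all randomised patients, when they cover only those registered before chemotherapy.

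**Working it through.** **Inputs.** From 15.3: 303 per arm. From 15.6: 20% loss, 264 evaluable and 0.274 SD (substudy 1); 70% yield and 230 evaluable (substudy 2); two-sided 0.05; the logistic effects listed above. Assumed: *f*, the share of each 303-patient arm registered after a prior cycle. The documents do not give it, so a range is shown.

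**Step 1: the plan's power at the plan's n.** For a two-sample t test with n per arm and difference d in SD units, the noncentrality is d√(n/2) on 2n − 2 degrees of freedom. At n = 264: 0.274 × √132 = 3.148, power 88.1%. That is close to the stated 90%, which would need about 281 per arm. The claim is therefore roughly reproduced at 264, with no slack.

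For the logistic statements, let λ be the log odds ratio per SD. Two standard formulas were used:
- Hsieh 1989: n = [z(α/2) + z(β)·exp(−λ²/4)]² (1 + 2pδ)/(pλ²), where p is the event probability at the biomarker mean and δ = [1 + (1 + λ²)exp(5λ²/4)]/[1 + exp(−λ²/4)].
- Hsieh 1998: power = Φ(√(n·p(1 − p))·|λ| − 1.96).

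Under the 1989 formula all six statements reproduce: response 95.5%, FFS 90.5% and OS 93.3% at 264; response 92.6%, FFS 90.9% and OS 93.8% at 230. The 1998 formula reproduces FFS and OS but gives response only about 80% and 74%. Since response depends so much on the formula, nothing below rests on it.

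**Step 2: the plan's n from the plan's inputs.**
- 303 × 0.80 = 242, not 264.
- 303 × 0.70 = 212, not 230.
- Working backwards, 264/0.80 = 330 and 230/0.70 = 329, so both figures fit a base of about 330 per arm.
- The 5% allowance in 15.3 for cancelled or ineligible patients does not close the gap: 303/0.95 = 319, and 80% and 70% of 319 are 255 and 223.

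With nobody barred, n = 242 gives noncentrality 0.274 × √121 = 3.014 and power 85.3%. The difference detectable with 90% power is 0.295 SD.

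**Step 3: add the exclusion.** Substudy 1 has n = 303 × (1 − f) × 0.80, and substudy 2 has n = 303 × (1 − f) × 0.70. Logistic cells show the 1989 / 1998 formula.

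| f | n, substudy 1 | t test, 0.274 SD | FFS 40→51% | OS 50→61% | n, substudy 2 | FFS 40→52% | OS 50→62% |
|---|---|---|---|---|---|---|---|
| 0% | 242 | 85.3% | 88 / 92% | 91 / 94% | 212 | 88 / 93% | 92 / 95% |
| 10% | 218 | 81.4% | 84 / 90% | 88 / 91% | 191 | 85 / 91% | 89 / 92% |
| 20% | 194 | 76.8% | 80 / 86% | 84 / 88% | 170 | 80 / 87% | 85 / 89% |
| 30% | 170 | 71.2% | 74 / 81% | 79 / 83% | 148 | 75 / 82% | 79 / 85% |

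The 90%-power detectable difference for the t test rises from 0.295 SD at f = 0 to 0.311, 0.330 and 0.353 SD.

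**Step 4: when the stated n is out of reach.** If every eligible patient consented and gave usable samples, 264 would be unattainable only when f exceeds (303 − 264)/303 = 12.9%, and 230 only when f exceeds (303 − 230)/303 = 24.1%.

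**Scale of f.** Only registrations from February 20, 2013 are affected. Section 15.3 gives 88 patients on the discontinued arm at November 20, 2012. Under 1:1:1 allocation that suggests about 88 on each other arm by then, leaving at most about 303 − 88 = 215 per arm exposed. The true number is somewhat smaller, because three more months of accrual preceded the change. On that upper bound, f = 10%, 20% and 30% correspond to at least 30/215 = 14%, 61/215 = 28% and 91/215 = 42% of later registrants.

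**The case against.** A reader might infer that the exclusion by itself makes the stated 90% power unattainable. The documents do not support that. They give neither an expected nor an actual share of prior-cycle entrants. By Step 4, 264 and 230 stay reachable at small shares if uptake is high, and Step 3 shows some FFS and OS statements holding 90% at f = 10% under one of the two formulas. Part of the shortfall is also unrelated to the exclusion, because it is already there at f = 0.

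It can also be said that the 20% allowance includes ineligibility, and that section 5.6 describes prior-cycle patients as not eligible for the companion studies, so the allowance may already cover them. The text does not settle this. Even on that reading, 80% of 303 is 242, so the 264 remains unsupported.

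The consequences are limited. Section 10.1.1 calls the first substudy's objectives exploratory, and 15.6 says the same of the second substudy's tests. The exclusion is stated clearly in three operative sections, so sites are unlikely to enrol wrongly. The third (ProGRP) substudy is sized at 150 to 200 patients and does not depend on inviting everyone.

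These points limit the scope and strength of the finding. They do not rescue the stated numbers.

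**Conclusion.** The point stands for the first two substudies. The part that needs no assumption is arithmetic: at the section's own loss and yield, 303 per arm gives about 242 and 212 evaluable. Power for 0.274 SD is then about 85% (88.1% at the stated 264), and the 90%-power detectable effect is about 0.295 SD.

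The exclusion can only lower these figures, by an amount that depends on an undocumented share. Assuming 10%, 20% or 30% of each arm barred and the 80% yield, power for 0.274 SD is about 81%, 77% or 71%. The 2-year FFS and OS statements also fall below 90% over most of that range. That 90% power cannot be delivered because of the exclusion is not shown. What is shown is that the stated numbers are unsupported and err in the favourable direction. The ProGRP substudy and the primary overall survival comparison are not affected.

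**What to change.** In section 15.6:

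1. Change the invitation sentence to read: *All patients registered before any chemotherapy will be invited*. This brings it into line with 5.6, 6.3 and 10.0.
2. Replace 264 and 230. Start from the number of patients per arm, out of 303, who registered before any chemotherapy; the radiotherapy start-time stratum records this. Apply the 80% and 70% yields to that number.
3. Restate power, or the 90%-power detectable effects, for substudies 1 and 2, and name the formula behind the logistic figures.
4. State that the biomarker results apply to patients registered before chemotherapy.

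No extra patients, samples or assays are needed. The cost is a short text revision and less favourable stated figures.

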6.3.1 Plasma Collection for both Correlative Science Studies (see [Section 10.1](#))

For patients who consent to participate, 20 ml of whole blood (in two 10 ml purple top tubes) will be collected at the following time points:

- Baseline (before treatment initiation)
- Day 1 of Cycles 2, 3 and 4 (pre-chemotherapy),
- At first follow-up after completion of all protocol treatment,
- At each post-treatment follow-up visit (Follow-up is every 3 months for 2 years, then every 6 months for 3 years, and then yearly. Note: If follow-up is completed more often than required a plasma sample is preferred by is not required.)
- At the time of recurrence.

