8.0 TREATMENT PLAN

Patients registered to CALGB 30610 prior to the start of cycle 1 protocol treatment will start therapy within 7 days of registration.

Questions regarding treatment should be directed to the Alliance Study Chair.

Protocol therapy will consist of 4 cycles of cisplatin and etoposide or carboplatin and etoposide chemotherapy administered every 21 days. Thoracic radiotherapy will begin either on the first day of the first cycle of chemotherapy OR on the first day of the second cycle of chemotherapy.

Patients may be registered to CALGB 30610 following one cycle of chemotherapy. Patients must receive the second cycle of therapy following registration, on day 22-24, so that the patient adheres to a 3-week treatment cycle. Patients not able to be treated within 3 days of day 22 should not be registered to CALGB 30610. For patients registered to CALGB 30610 after 1 cycle of chemotherapy, the thoracic radiotherapy must begin with the second cycle of chemotherapy (the first cycle of protocol chemotherapy after the patient was registered). Additionally, the cycle of chemotherapy given prior to registration will be considered “cycle 1.” Therefore, patients registered following 1 cycle of chemotherapy will receive three cycles of therapy after registration.

The original design was a randomized phase III trial including two experimental treatment arms (70 Gy once daily radiotherapy and 61.2 Gy concomitant boost radiotherapy) and a standard treatment arm (45 Gy twice daily radiotherapy). An interim analysis, conducted after accrual of a pre-determined number of patients, selected one experimental arm based upon a comparison of treatment related toxicity. The most toxic experimental arm, which was Arm C, was discontinued, and the trial now compares standard therapy to the selected experimental regimen.

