10.1 Correlative Science Substudies (CALGB 150712)

10.1.1 Exploratory Investigation of Circulating Biomarkers

The goal of the first correlative study is to use the multiplex bead assay to systematically examine potential blood-based biomarkers of anti-tumor response and therapeutic resistance to the two chemoradiotherapy regimens, with a focus on circulating cytokines and angiogenic factors.

This correlative study will be performed at MD Anderson Cancer Center in the laboratory of [REDACTED]

Rationale: Previous studies have established that both the tumor response to radiotherapy and radiation-induced gastrointestinal toxicity are dependent on the induction of tumor endothelial apoptosis and angiogenesis [27, 28]. Furthermore, radiation induces compensatory pathways, including hypoxia inducible factor-1 (HIF-1), which affect endothelial survival and tumor radiosensitivity through mediators such as VEGF and basic

FGF [29]. Interestingly, the sequencing and frequency of radiotherapy had a significant impact on the activation of these pathways [29]. Assessing the treatment-induced changes in circulating angiogenic factors and cytokine expression, particularly HIF-regulated factors, may therefore provide important information regarding the tumor response to different treatment regimens. In this study we will investigate a biomarker profile consisting of circulating potential blood-based biomarkers of response and resistance, including proangiogenic cytokines (i.e., EGF, bFGF, IL-8) and markers of endothelial damage (soluble E-selectin, soluble VEGFR-2).

Objectives: The exploratory objectives of the correlative study are:

1. To determine whether the baseline biomarker profile, or changes in the profile during treatment, correlate with clinical outcome as judged by objective response rate, progression free survival, and overall survival.
2. To compare the changes in the biomarker profile between the two treatment arms.

Hypotheses

1. Higher-dose, accelerated radiation therapy will cause a larger rise in circulating markers of endothelial damage than hyperfractionated and accelerated radiotherapy (HFXART) due to a greater induction of tumor endothelial apoptosis.
2. Other circulating biomarkers may be useful for helping to identify patients most likely to benefit from therapy, monitor antitumor responses, and understand mechanisms of therapeutic resistance.

Method for Multiplex Bead Assay

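### Section 15.6 does not say which draw carries the between-arm biomarker comparison, and its only listed on-treatment draw (day 21) has no radiation in one start-time group and the reverse dose order in the other

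*Combined protocol and SAP*

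**What the plan says.** **Hypothesis.** Section 10.1.1 states: "Higher-dose, accelerated radiation therapy will cause a larger rise in circulating markers of endothelial damage than hyperfractionated and accelerated radiotherapy". Section 15.6 makes this the first primary objective of the first correlative substudy.

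**Draws.** The opening paragraph of section 15.6 says samples "will be collected at baseline (before treatment initiation), day 21 (pre-chemotherapy), at first follow-up after completion of all protocol treatment", and at recurrence. Section 6.3.1, which covers the plasma for the correlative studies, asks for more. Its on-treatment entry is "Day 1 of Cycles 2, 3 and 4 (pre-chemotherapy"), followed by the first post-treatment visit, every later follow-up visit and recurrence.

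**Test.** The power paragraph for the first substudy says "we assume the transform of biomarker count difference between post-treatment initiation and baseline follows approximately a normal distribution" and plans a two-sample t test. The Analytic Methods text of 15.6 keeps that test, with a rank-sum fallback. Neither place names the visit from which the change is taken, and neither mentions radiotherapy start.

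**Radiotherapy start.** Section 8.0: "Thoracic radiotherapy will begin either on the first day of the first cycle of chemotherapy OR on the first day of the second cycle". Start time is a stratification factor for randomisation (sections 5.5, 15.2 and 15.3). Sections 5.6, 6.3 and 10.0 exclude from the substudy patients registered after a prior cycle. Cycle-1 and cycle-2 starters are therefore its whole population.

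**Use as a predictor.** For the second substudy, section 15.6 lists the changes at day 21, at first follow-up and at recurrence as predictors of response, 2-year FFS and 2-year OS. These are analysed by arm but not by radiotherapy start.

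**The concern.** The hypothesis concerns the effect of radiation dose. Its test therefore needs a draw at which the two arms have received different radiation in the hypothesised order. The draw list in 15.6 has one on-treatment entry, day 21. With 21-day cycles and a pre-chemotherapy draw, that is effectively day 1 of cycle 2, when cycle-2 starters have not begun radiotherapy.

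With no visit fixed, the analyst can choose among draws at which the dose order is null, reversed or as hypothesised, and that choice alone could change the conclusion. If day 21 were chosen, a null or reversed result could be read as biology when it came from sample timing. The predictor models have a related problem: the day-21 change reflects chemotherapy alone in some patients and chemoradiation in others, and start time is not a named term.

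**Working it through.** **Inputs.** Section 8.2.2: arm A receives 1.5 Gy twice daily, 5 days a week, 45 Gy in 30 fractions (15 treatment days at 3 Gy); arm B receives 2 Gy once daily, 5 days a week, 70 Gy in 35 fractions (35 treatment days at 2 Gy). Section 8.1: 21-day cycles. Section 15.6: 264 evaluable per arm, 0.274 SD, two-sided 0.05, stated power 90%. Arm C is left out because it was discontinued.

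**Step 1. Planned cumulative dose at each draw.** Dose = min(5 × weeks since radiotherapy start, total treatment days) × daily dose, assuming no interruptions. At three weeks, arm A has 15 × 3 = 45 Gy and arm B has 15 × 2 = 30 Gy. At six weeks, arm A stays at 45 Gy and arm B has 30 × 2 = 60 Gy.

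| Draw | Cycle-1 starters, A vs B (Gy) | Cycle-2 starters, A vs B (Gy) |
|---|---|---|
| Day 21 / day 1 of cycle 2 | 45 vs 30 | 0 vs 0 |
| Day 1 of cycle 3 | 45 vs 60 | 45 vs 30 |
| Day 1 of cycle 4 | 45 vs 70 | 45 vs 60 |
| First follow-up after treatment | 45 vs 70 | 45 vs 70 |

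At day 21 neither group has the hypothesised order. At day 1 of cycle 3 the order differs between the groups. At day 1 of cycle 4 and at first follow-up, arm B leads in both.

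**Step 2. The plan's own power figure.** Noncentrality = d × √(n/2) = 0.274 × √132 = 3.15. With 526 degrees of freedom and two-sided 0.05, power is 88.1% (88.3% by normal approximation), within two points of the stated 90%. A full 90% would need 280 per arm, or an effect of 0.282 SD at 264 per arm.

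**Step 3. Power if day 21 were the test visit.** Let f be the share of cycle-2 starters. The documents do not give it, so it is varied. Those patients contribute no radiation difference at day 21, so the average effect is 0.274 × (1 − f), with the SD held at 1.

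| f (assumed) | Average effect (SD) | Power, 264 per arm |
|---|---|---|
| 0% | 0.274 | 88% |
| 25% | 0.2055 | 65% |
| 50% | 0.137 | 35% |
| 75% | 0.0685 | 12% |

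These figures are generous: they credit cycle-1 starters with the full effect in the hypothesised direction, although at that draw arm B has had 15 Gy less than arm A.

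**The case against.** The strongest reply is that no text ties the between-arm test to day 21. A reader might infer from the 15.6 draw list that the comparison relies on day 21 and so cannot test its hypothesis. The documents do not support that. The same sentence of 15.6 goes on to the first post-treatment follow-up, where planned dose is 45 vs 70 Gy in both groups. Section 6.3.1 requires draws at cycles 3 and 4, and the ProGRP text within 15.6 itself uses values after each cycle. This part of the reply stands.

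It does not remove the problem. First follow-up is available but is not a clean substitute. The timetable in section 10.2.2 puts week 12 from radiotherapy start 9 weeks after the end of the 45 Gy course and 5 weeks after the end of the 70 Gy course, so recovery time differs by arm. Section 8.2.9 starts cranial irradiation about 3 to 6 weeks after the last chemotherapy cycle, so that draw may follow it.

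Three further replies have weight:

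- Randomisation is stratified by start time, so pooling the two groups dilutes the contrast rather than biasing it through imbalance.
- The Analytic Methods allow adjustment for baseline confounders in the outcome models, although start time is not named.
- Section 10.1.1 calls the objectives exploratory, and the trial's efficacy and safety conclusions are untouched.

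Finally, cumulative dose need not be what drives the markers. Section 10.1.1 itself says that sequencing and frequency of radiotherapy matter, and the documents give no marker kinetics. That is a reason to justify the chosen visit, not to leave it open.

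**Conclusion.** The point holds as a gap in specification with a definite consequence. Sections 6.3.1 and 15.6 list different draws; the primary between-arm change score has no visit and no link to radiotherapy start; and the only on-treatment draw in the 15.6 list would give a contrast with no radiation difference in cycle-2 starters and a reversed dose order in cycle-1 starters. Separately, and whichever visit is chosen for the arm comparison, the second substudy's day-21 predictor pools chemotherapy-only with chemoradiation changes.

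The dose table follows from the protocol schedules, assuming delivery on time. The fall in power from 88% to 65%, 35% or 12% is conditional twice over: on day 21 being the test visit, which the plan does not say, and on the assumed shares of cycle-2 starters. It shows the risk and is not an estimate of the substudy's actual power. The issue should be corrected, but it is confined to a correlative substudy.

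**What to change.** Revise section 15.6 as follows:

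1. Replace its draw list with that of section 6.3.1.
2. Index draws by time from radiotherapy start, and stratify the between-arm comparison by radiotherapy start time.
3. Exclude the day-1-of-cycle-2 draw of cycle-2 starters from the between-arm radiation contrast.
4. Pre-specify one primary visit relative to radiotherapy start, supported by a mixed model over all draws. One option is six weeks after radiotherapy start: day 1 of cycle 3 for cycle-1 starters and day 1 of cycle 4 for cycle-2 starters, with planned dose 45 vs 60 Gy in both. Its limit should be stated: arm A finished radiation about three weeks earlier while arm B is in week 6 of 7. Time since last radiation differs between the arms at any visit, so the choice needs a stated reason.
5. Include radiotherapy start time in every model that uses the day-21 change as a predictor of response, FFS or OS.

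This needs no new patient, no new sample and no change to treatment. The cost is the wording and the assay of banked cycle-3 and cycle-4 aliquots.
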